5.2.4 Electrocardiogram

5.2.4.1 12-lead resting ECG

ECG measurements will always precede blood sampling to avoid impact of sampling on the ECG results.

In order to achieve a stable heart rate at rest and to assure high quality recordings at comparable resting phases, all ECGs will be recorded for a 10-sec duration after the patients have rested for at least 5 min in a supine position. The site personnel will be instructed to assure a relaxed and quiet environment so that all patients are at complete rest during the recordings. ECG assessment will always precede all other study procedures of the same time point (except blood drawing from an intravenous cannula which is already in place) to avoid impact of sampling on the ECG quality.

Electrode placement will be performed according to the method of Wilson, Goldberger and Einthoven.

Triple ECGs (recorded within 180 sec) will be recorded at the second screening visit (V2). At all other time points single ECGs will be recorded.

All locally printed ECGs will be evaluated by the investigator or a designee.

ECGs may be repeated for quality reasons (like alternating current artefacts, muscle movements, electrode dislocation). For time point with triple ECGs, all three single ECGs will be repeated.

Additional (unscheduled) ECGs may be collected by the investigator for safety reasons. These ECGs are assigned to the prior scheduled time point.

For the inclusion or exclusion (see [Section 3.3](#)) of a patient and for the assessment of cardiac safety during the study, the QT and QTcF according to Fridericia's formula

($QTcF = QT / RR^{1/3}$), and generated by the ECG machines or their manual corrections by the investigators will be used.

Proprietary confidential information © 2016 Boehringer Ingelheim International GmbH or one or more of its affiliated companies

Abnormal findings will be reported as AEs (during the trial) or baseline conditions (at pre-treatment) if judged clinically relevant by the investigator. Any ECG abnormalities will be monitored carefully and, if necessary, the patient will be removed from the trial and will receive the appropriate medical treatment.

Assessed ECGs will comply with the ICH E14 guidance document and supplements [[R05-2311](#), [R13-0801](#), [R13-4095](#)] as well as the FDA requirements for annotated digital ECGs [[R09-4830](#)].

5.2.5 Assessment of other safety parameters

5.2.5.1 Vital signs

Vital signs evaluations will be performed at visits as shown in the [flow chart](#). This includes body weight, temperature, pulse rate, systolic/diastolic blood pressure.

Body weight measurements should be done on the same scale for each patient. In order to get comparable body weight values, it should be performed in the following way:

- fasting (except for the screening visits)
- after the urine sampling (body weight after bladder voiding)
- shoes and coat/jackets should be taken off
- pockets should be emptied of heavy objects (i.e. keys, coins etc.)

Body temperature will be measured using a standard device. All recordings for a given patient should be made using the same instrument and at the same area (ear, mouth...).

Pulse rate, and blood pressure will be measured after patients have been sitting comfortably for at least five minutes. All recordings should be made using the same type of blood pressure recording instrument on the same arm if possible.

Measurement of vital signs should precede blood sampling to avoid the impact of blood sampling on the vital measurements.

At dosing visit (V3), vital signs evaluations will be performed pre-dose.

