Based on the preceding FIH study, no specific drug-related risks are anticipated. Still, the following safety measures are/will be applied in this study in order to minimize the risk for the GPP patients:

- The IV administration allows to immediately discontinue further drug administration should any safety concern arise (please refer to [Section 4.1.4](#)).
- BI 655130 will be administered in a hospital setting and patients will be under close medical observation during their hospitalization (see [section 6.2](#)), as well as after their discharge and until the end of observation period. Safety will be closely monitored during site visits.
- Patients will be closely monitored for signs and symptoms of hypersensitivity reactions for 4 hours after the infusion at Visit 3. Hypersensitivity reactions should be treated according to medical standards.
- Extensive safety laboratory testing will be performed ([Table 5.2.3:1](#)).
- The investigator will have the possibility to treat the patient with a rescue medication of his/her choice. The decision to use a rescue medication will be based on the severity and progression of the disease (please refer to [section 4.2.1](#)).

Currently there are no data available to suggest interactions of BI 655130 [[c03320876-01](#)].

Retinoids (such as acitretin) and methotrexate will be permitted as background therapy (please refer to section 4.2.1).

Although rare, a potential for drug-induced liver injury (DILI) is under constant surveillance by sponsors and regulators. Therefore, this study requires timely detection, evaluation, and follow-up of alterations in selected liver laboratory parameters to ensure patients' safety.

Based on the findings in the nonclinical studies conducted to date and in accordance with international regulatory guidelines, the inclusion of women of childbearing potential in this study is justified [[c03320876-01](#)]. To minimize the risk of unintentional exposure of an embryo or fetus to the investigational drug, women of childbearing potential must agree to

Proprietary confidential information © 2016 Boehringer Ingelheim International GmbH or one or more of its affiliated companies

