4.1.4 Drug assignment and administration of doses for each subject

The treatment to be evaluated is outlined in [Table 4.1.4: 1](#) below. It will be assigned to each patient after the completion of the inclusion visit and verification of all inclusion and

Proprietary confidential information © 2016 Boehringer Ingelheim International GmbH or one or more of its affiliated companies

exclusion criteria. The assignment will occur in an open label fashion via Interactive Response Technology (IRT).

All included patients will receive the BI 655130 on Day 1. For further details concerning timing see [Flow Chart](#). Start- and end time of the infusion will be recorded.

Detailed instructions for the preparation of the infusion solution, the volume to be administered and the infusion rate is provided in the ISF.

After preparation, the solution for infusion may be stored at 2 - 8°C for up to 24 hours. After removal from 2 - 8°C storage or preparation, the solution must be administered within 60 minutes if stored at $\leq 25^{\circ}\text{C}$. Do not freeze.

Chemical and physical in-use stability has been demonstrated for 60 minutes at room temperature $\leq 25^{\circ}\text{C}$. In addition the time for infusion must not exceed 240 minutes at $\leq 25^{\circ}\text{C}$.

From a microbiological point of view the drug should be used immediately. If not used immediately, the in-use storage times and conditions prior to use are the responsibility of the user, and would normally not be longer than 24 hours at 2 - 8°C (36 - 46°F), unless preparation has taken place in controlled and validated aseptic conditions.

In all patients, the infusion solution will be intravenously administered over a period of 60 minutes. Infusion time can be extended up to 240 minutes provided that the maximum time between the start of preparation and completion of administration of the solution to the patient does not exceed 300 minutes (5 hours).

In case of safety concerns, e.g. due to infusion reactions, it is at the discretion of the investigator or his/her designee to adapt the infusion scheme, including but not limited to slowing down the infusion rate, stopping of the infusion and provided no further safety concern exists restarting at a slower rate. In any case, the total duration of infusion should not exceed 240 minutes (4 hours). Further based on medical judgment he/she will provide medications such as steroids, etc. as needed.

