5.2.5.2 Medical examinations

At the inclusion visit, the medical examination will include documentation of patient information, informed consent, demographics including height, smoking and alcohol history, relevant medical history and concomitant therapy, review of inclusion and exclusion criteria, review of vital signs (BP, PR, body weight and temperature), 12-lead ECG, laboratory tests, and a physical examination. At the End-Of-Trial examination, it will include review of vital signs, 12-lead ECG, physical examination, assessment of psoriatic lesions, and of the presence of edema.

Proprietary confidential information © 2016 Boehringer Ingelheim International GmbH or one or more of its affiliated companies

Physical examinations will be performed at visits as described in the [Flow Chart](#). Physical examination will include general appearance as well as evaluation of all relevant organ systems. Clinically relevant abnormal findings will be reported as baseline conditions or AEs.

Patients should be closely monitored for signs and symptoms of hypersensitivity reactions for approximately 4 hours after the infusion at Visit 3. Hypersensitivity reactions should be treated according to medical standards.

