6.2 DETAILS OF TRIAL PROCEDURES AT SELECTED VISITS

Study procedures to be performed at each visit are listed in the flow chart and the respective protocol sections. Refer to [Section 5](#) for explanations of procedures. Additional details on procedures at selected visits are provided below.

Included patients must be hospitalized for at least 4 days following the study drug administration. Patients will perform Visits 2 to 7 as inpatients. Visits 8 to 14 can be ambulatory or as inpatient if the patient is still hospitalized.

Measurement of vital signs should precede blood sampling and be assessed pre-dose at dosing visit.

The following sequence of procedures at each visit (where applicable) is recommended:

1. FACIT-Fatigue scale, pain VAS, and PSS
2. AE/local tolerability (at V3, local tolerability will be evaluated after the infusion) and concomitant therapy collection
3. Physical examinations / Vital signs / Body weight and temperature
4. GPPGA, GPPASI, CGI-I, presence of edema, pustular BSA
5. Photographs of skin lesions

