6.2.2 Treatment Visit (V3) and observation period

Treatment Visit 3 should be performed the day after Visit 2.

The BI655130 will be administered only at Visit 3. The observation period is from Visit 4 to EOT Visit (V14).

All procedures described in the Study Flow Chart and [PK Flow Chart](#) for this visit will be performed.

Study measurements and assessments scheduled to occur ‘before’ trial medication administration on Day 1 are to be performed and completed within a 4 h-period prior to the trial drug administration (including blank values for PK, ADA and biomarkers).

For information regarding laboratory tests, ECG, vital signs, and physical examination, refer to [Sections 5.2.3](#) to [5.2.5](#).

Fasting condition is not required for blood sampling. Pharmacogenomic genotyping for targeted GPP causing mutations (IL36RN, CARD14, AP1S3) will be performed in all patients (for details see [Sections 5.6.2](#) and [5.6.3](#)). DNA banking is optional and will only be performed in patients who give their consent for it.

Skin lesions photographs will be taken at all visits on site except visits 7 and 8. Skin biopsies will be performed at visits 3, and 9 (one additional biopsy at visit 10 is optional). For indications, refer to ISF.

Skin biopsies and venipuncture (i.e. safety laboratories, PK, ADA, biomarkers) should be the last procedure prior to study drug administration.

Study drug allocation via IRT and administration of study medication should be the last activity at Visit 3.

A urine pregnancy test will be performed at Day 28 (Visit 12), Day 56, Day 84 (Visit 13), Day 112, and Day 140 (Visit 14). The patient will inform the site of the results of the tests performed at Day 56 and Day 112 by phone.

Proprietary confidential information © 2016 Boehringer Ingelheim International GmbH or one or more of its affiliated companies

All abnormal values (including laboratory parameters) that are judged clinically relevant by the investigator will be monitored using the appropriate tests until a return to a medically acceptable level is achieved.

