## **6.7 BASELINE, TIME WINDOWS AND CALCULATED VISITS**

Measurements reported with date and time and taken prior to start of administration of trial treatment will be considered pre-treatment values. Measurements reported with a date only (and no time) and taken on the day of administration of trial treatment will also be considered pre-treatment values. These pre-treatment values will be assigned to visits according to the nominal visit number as recorded on the eCRF or as provided by the laboratory.

Baseline is defined as the last measurement collected prior to the start of administration of the trial treatment.

Measurements taken after start of administration of trial treatment will be considered values of the on-treatment period or follow-up values, based on the definition in [Section 6.1](#), and will be assigned to visits for statistical analysis, if applicable, as defined below.

The assessment of injection site reactions (scheduled for Visit 3 and Visit 4) will be handled differently to other by-visit endpoints, because the Visit 3 assessment is not a pre-treatment assessment, but is planned after injection of trial treatment, therefore representing an on-treatment measurement (i.e., both assessments are on-treatment assessments). Assessments at or after start of administration of trial treatment will be assigned to the nominal visit number as recorded on the eCRF, i.e. no time windows will be applied for analysis of this data.

Analysis of AE data and of rescue use will not be based on visits, therefore, no assignment to time windows will be necessary.

All other safety, efficacy and biomarker measurements will be assigned to visits based on time windows around the planned visit dates, defined relative to the day of trial treatment (which is scheduled for Visit 3). These time windows are defined in [Table 6.7: 1](#).

Table 6.7: 1 Time windows for assignment of efficacy, safety lab, vital signs, biomarker, and RNA sequencing measurements to visits for statistical analysis

Visit number	Visit label	Planned day	Time window		
			Window	Start (inclusive)	End (inclusive)
4	Week 1, Day 2	Day 2	exact day	Day 2 A	Day 2
5	Week 1, Day 3	Day 3	exact day	Day 3	Day 3
6	Week 1, Day 4	Day 4	exact day	Day 4	Day 4
7	Week 1, Day 5	Day 5	exact day	Day 5	Day 5
8	Week 1, Day 6	Day 6	exact day	Day 6	Day 6
9	Week 1, Day 7	Day 7	+ 3 days	Day 7	Day 10
10	Week 2	Day 14	+/- 3 days	Day 11	Day 17
11	Week 3	Day 21	+/- 3 days	Day 18	Day 24

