For final Week 4 analysis					
12	Week 4	Day 28	- 3 days/+ 10 days	Day 25	Minimum of (cut-off B ; Day 38)
For final analysis of entire trial					
12	Week 4	Day 28	- 3 days/+ 10 days	Day 25	Day 38
13	Week 12	Day 84	+/- 14 days	Day 70	Day 98
14	Week 20 (follow-up)	Day 142 D	exact day to last value	Day 142	Day of last value C

All days are counted relative to the day of treatment, which is defined as Day 1.

A Note that measurements made at Day 1 and assigned to the on-treatment period (because mistakenly made after start of infusion of trial treatment) via assessment on date and time (i.e. safety laboratory, GPPASI, GPPGA) will not be assigned to Visit 4. Such data will be listed only.

B The cut-off date will be specified in the data cleaning plan for the 4-week analysis.

C Note that measurements assigned to the Week 20 (follow-up) visit are intended to represent follow-up measurements, i.e., made after the end of the on-treatment period (as defined in [Table 6.1: 1](#)).

D Planned day per CTP is Day 140, which would still be during the on-treatment period, as REP is defined to be 140 days.

Repeated and unscheduled efficacy, safety and biomarker measurements will be handled similarly to scheduled measurements and will also be assigned to a time window depending upon the date of measurement.

Only one observation per time window will be selected for statistical analysis at a particular visit – the value which is closest to the protocol planned visit day will be selected. If there are two observations which have the same difference in days to the planned day, but which are not measured on the same day, the later value will be selected. If there are two observations on the same day, the worst value will be selected.

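### A vital-sign reading taken after dosing on Day 1 and recorded without a clock time would be classed as pre-treatment and could become baseline (minor)

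*Protocol*

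**What the plan says.** **Schedule.** Protocol 5.2.5.1 states "At dosing visit (V3), vital signs evaluations will be performed pre-dose", and Protocol 6.2 repeats it: "Measurement of vital signs should precede blood sampling and be assessed pre-dose at dosing visit". In the Flow Chart the next vital signs are at Visit 4 (Day 2).

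**What happens after dosing.** Protocol 2.3 says "Patients will be closely monitored for signs and symptoms of hypersensitivity reactions for 4 hours after the infusion at Visit 3", and Protocol 5.2.5.2 says much the same: "Patients should be closely monitored for signs and symptoms of hypersensitivity reactions for approximately 4 hours after the infusion at Visit 3". Neither names vital-sign time points. Protocol 6.2 places the Visit 3 local tolerability check after the infusion. Protocol 6.2.2 nevertheless says "Study drug allocation via IRT and administration of study medication should be the last activity at Visit 3".

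**Classification of Day 1 values.** SAP 6.7 says "Measurements reported with a date only (and no time) and taken on the day of administration of trial treatment will also be considered pre-treatment values". It defines baseline as the last measurement before the start of administration, and it handles repeated and unscheduled safety measurements like scheduled ones. Footnote A to SAP Table 6.7:1 deals with Day 1 values placed on-treatment "via assessment on date and time (i.e. safety laboratory, GPPASI, GPPGA"; vital signs are not in that list.

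**Exemptions.** SAP 6.7 treats the Visit 3 injection site assessment as on-treatment. SAP 6.1 and 7.8.1 do the same for any adverse event on the dosing day, because no start time is collected. There is no such exemption for vital signs.

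**Use.** SAP 7.8.3 summarises differences from baseline, the on-treatment last, minimum and maximum values, and a temperature shift table at 37.5 °C. Under SAP 6.7 the on-treatment extremes use all on-treatment values, whether or not they fall in a visit window.

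**The concern.** The protocol foresees acute reactions on the dosing day: Protocol 4.1.4 lets the investigator slow or stop the infusion, and close observation follows. A blood pressure, pulse or temperature taken in those hours would be an unscheduled reading. If it carries a date but no time, the SAP default places it before treatment.

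The same reaction could then appear as an on-treatment adverse event and as a pre-treatment vital sign. The reading would be missing from the on-treatment extremes, and it might become the reference value for later visits. Vital signs are a named safety criterion in Protocol 5.2.1, and with 6 to 10 patients a single wrong baseline shows in the tables. Vital signs are also part of the Week 4 analysis, whose results SAP 3 allows to be published.

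**Working it through.** There is no figure in the plan to reproduce. The check traces the rules and adds simple arithmetic.

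**1. Length of the interval.** Planned infusion time (Protocol 4.1.4): "the infusion solution will be intravenously administered over a period of 60 minutes". Longest allowed infusion (same section): 240 minutes. Monitoring after the infusion (Protocol 2.3): 4 hours = 240 minutes.

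- Planned: 60 + 240 = 300 minutes (5 hours)
- Longest: 240 + 240 = 480 minutes (8 hours)

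Over this span observation is described but no vital sign is scheduled.

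**2. Where an unscheduled Day 1 reading goes.**

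- *With a clock time after infusion start:* SAP 6.7 makes it on-treatment. It belongs to no visit window, because the windows start at Day 2, but it counts in the on-treatment minimum and maximum.
- *With a date only:* SAP 6.7 makes it pre-treatment. It leaves the on-treatment minimum and maximum in every case. It is then a candidate for baseline alongside the scheduled pre-dose reading.

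Two date-only values on the same day cannot be ordered, and the SAP does not say which is the last. Its worst-value tie rule is written for selection within a time window, so it does not settle the choice on Day 1.

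**3. Illustration (invented values).** Temperature is 37.0 °C pre-dose, 38.5 °C two hours after the infusion, and 37.0 °C on Day 2 and later.

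| Quantity | Clock time recorded | Date only, pre-dose value kept as baseline | Date only, later value taken as baseline |
|---|---|---|---|
| Baseline | 37.0 | 37.0 | 38.5 |
| On-treatment maximum | 38.5 | 37.0 | 37.0 |
| Maximum minus baseline | +1.5 | 0.0 | −1.5 |
| Day 2 minus baseline | 0.0 | 0.0 | −1.5 |
| Shift at Day 2 (37.5 °C) | below to below | below to below | at or above to below |

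The rise is lost in both date-only columns. In the last one it becomes an apparent improvement.

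**4. Weight of one patient.** Share of the treated set: 1/10 = 10%; 1/6 = 16.7%. If one patient's baseline is too high by d, the mean baseline rises, and the mean change falls, by d/n. For an assumed d of 1 to 2 °C:

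- n = 10: 1/10 = 0.10 to 2/10 = 0.20 °C
- n = 6: 1/6 = 0.17 to 2/6 = 0.33 °C

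**The case against.** **The form is not shown.** No document says that vital signs lack a clock time; footnote A only implies it by omission. SAP Table 6.1:1 sets the phases for vital signs by date and time, but it does so for adverse events too, which carry no start time, so it does not decide the matter. If a time is recorded, the classification problem disappears. This stands, and makes the point conditional.

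**Several things must coincide.** A site must take an extra reading, enter it as vital-sign data without a time, and the programming must pick it as the last value. A reading known to follow the infusion also falls outside the literal baseline definition. A reader might infer that such a reading will become baseline; the SAP supports only that it could. The loss from the minimum and maximum does not depend on that choice.

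**The safety signal is captured elsewhere.** A reader might infer that reactions escape the primary endpoint. They do not: Protocol 5.2.2.1 and SAP 7.8.3 have clinically relevant vital-sign changes recorded as adverse events, and any event on Day 1 is on-treatment. Individual values are also listed. This stands and limits the harm to descriptive tables.

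**The rule is not universal.** It would be too broad to say that every date-only Day 1 record is pre-treatment, given the exemptions for adverse events and injection site reactions.

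**The Visit 3 wording may not conflict.** The sentence in Protocol 6.2.2 about drug administration coming last follows one about the final procedures before dosing, so it plausibly orders the pre-dose steps only. Monitoring for signs and symptoms is compatible with a pre-dose vital-sign record. A reader might infer a flat contradiction, or that patients go unobserved; the text supports neither. What remains is wording that, read literally, sits badly with activities placed after the infusion at the same visit.

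**Conclusion.** The point holds as a minor one. SAP 6.7 has no rule that keeps an unscheduled, date-only vital sign taken after infusion start out of the pre-treatment period, although it makes that provision for two other kinds of Day 1 data. On the assumption that vital signs carry no clock time, such a reading is lost from the on-treatment extremes and may become baseline for the changes and the temperature shift table. The size is one patient in 6 to 10 for each occurrence (10% to 16.7%); the documents give no basis for saying how often it would occur. The effect is confined to the descriptive vital-sign summaries. The documents do not support a claim that the primary endpoint is at risk, and the lack of scheduled post-infusion vital signs is a clinical design choice on which this point takes no position.

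**What to change.** 1. **Data collection.** Record a clock time for any Day 1 vital sign and classify it against the start of infusion.
2. **SAP 6.7.** Limit vital-sign baseline to readings taken before infusion start or, where no time is recorded, to the scheduled pre-dose Visit 3 record. Assign all other Day 1 vital signs to the on-treatment period for the minimum, the maximum and the listing. Say this explicitly, because footnote A restricts its own Day 1 on-treatment values to listings and could be read across to vital signs.
3. **Protocol wording.** Reconcile the pre-dose and sequencing statements in 5.2.5.1, 6.2 and 6.2.2 with the post-infusion monitoring in 2.3 and 5.2.5.2 and the post-infusion local tolerability check in 6.2. Which post-dose readings are needed, if any, is the sponsor's clinical decision.

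The cost is one time field on the form, a sentence or two in the SAP and a wording clarification in the protocol. No extra visit or patient is needed.
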